5.1.5. Analysis window

Summary will be based on the visits filled in eCRF according to protocol predefined, with no need to consider unscheduled visits.

In the case that the scheduled protocol visit is missing, or one examination is missing within the scheduled visit or the result is invalid, the unscheduled visit closest to the scheduled protocol visit will be considered as the protocol visit. If the time to the scheduled visit is equal for two unscheduled visits, the later scheduled visit will be used as the protocol visit. All the protocol visits will be scheduled in order. Once one unscheduled actual visit has been defined as one protocol visit, it will be no more defined for the other protocol visit. When analyzing by visit, the statistical analysis will be performed in accordance with the time point for the scheduled protocol visits, i.e., there is no need to present the time points for unscheduled visits.

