Vital signs	√	√	√	√	Including blood pressure, heart rate, body temperature, respiratory rate. It will be conducted within 72 hours prior to each administration.

Items	Treatment period (One treatment cycle is 42 days)				Comment
	D1 ^[3] (±3 days)	D15 (±3 days) (Group A)	D22 (±3 days) (Group B)	D29 (±3 days) (Group A)	
Concomitant medications/treatments	√	√	√	√	
Collection of AE	√	√	√	√	Including symptoms and signs.
12-Lead ECG					Performed according to local standard during the study, when clinically indicated.
Echocardiography					Performed according to local standard during the study, when clinically indicated.
Hematology	√	√	√	√	Including complete blood cell count and category (white blood cell, red blood cell, lymphocyte, monocyte, neutrophil, basophil, eosinophil, hemoglobin), platelet count. The test will be conducted within 72 hours prior to each administration.
Urinalysis	√	√	√	√	Including white blood cell, red blood cell, and urine protein. The test will be conducted within 72 hours prior to each administration. If urine protein is ≥ 2+, 24 hours urine protein quantification must be detected additionally.
Blood biochemistry	√	√	√	√	Including hepatic function (ALT, AST, TBIL, ALP), renal function (BUN or serum urea level), albumin, creatinine, amylase (lipase must be detected additionally if amylase is abnormal and clinically significant), blood glucose, and LDH. The test will be conducted within 72 hours prior to each administration.
Blood electrolytes	√	√	√	√	Including K ⁺ , Na ⁺ , Ca ⁺⁺ , Mg ⁺⁺ , Cl ⁻ . The test will be conducted within 72 hours prior to each administration.
Coagulation function ^[4]	√				INR and/or PT (if INR cannot be collected, PT will be used as judgment basis). The test will start from Cycle 2, and will be finished at D1 of each cycle.
Alpha fetoprotein ^[4]	√				The test will start from Cycle 2, and will be finished at D1 of each cycle.
Thyroid function ^[4]	√				TSH, FT4 and FT3 will be detected on D1 of each cycle from Cycle 2.
Virology ^[4]	√				The test will start from Cycle 2, and will be finished at D1 of each cycle. HBV-DNA (PCR) will be detected for those with HBV infection; HCV-RNA will be detected for those with HCV infection.

Items	Treatment period (One treatment cycle is 42 days)				Comment
	D1 ^[3] (±3 days)	D15 (±3 days) (Group A)	D22 (±3 days) (Group B)	D29 (±3 days) (Group A)	
Efficacy assessments					

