7.2.2 Criteria for dose delay

The dose should be delayed if the following conditions occur:

- Any \geq Grade 2 treatment-related non-cutaneous AE, except Grade 2 treatment-related fatigue or laboratory abnormalities;
- Any Grade 3 treatment-related cutaneous AE;
- Any Grade 3 treatment-related laboratory abnormalities, except Grade 3 abnormal amylase or lipase unrelated with the symptoms and clinical manifestations of pancreatitis;
- The administration will be delayed if the following AST or ALT abnormalities occurs:
 - AST and ALT at baseline are within normal range, and Grade 2 treatment-related adverse events occur ;
 - AST or ALT at baseline elevates no greater than Grade 1, and Grade 3 treatment-related adverse events occur;
 - AST or ALT at baseline elevates no greater than Grade 2, and treatment-related elevated AST or ALT reaches > 2 times the baseline or either AST or ALT reaches $> 8 \times \text{ULN}$ (whichever is lower).

- The administration needs to be delayed for any AE, laboratory examination abnormalities or complications, as judged by investigators;

Subjects who need delayed dose should be monitored every week, and the frequency of monitoring can be increased when clinically indicated. It is recommended to monitor liver function every three days, until the highest value of AST or ALT starts to decrease. When meeting the criteria for resumption of medication (see Section 7.2.3), the investigational drug can be resumed.

Tumor evaluation still needs to proceed for all the subjects as required in the protocol, regardless of dose delay.

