5.5.3. Laboratory evaluations

Baseline is defined as the last measurement prior to first dose. The laboratory data will be summarized using descriptive statistics according to Hengrui's Statistical Analysis Reporting Standards, including but not limited to:

- Incidence of abnormalities by item and parameter;
- Shift table and listing of changes from baseline (normal/abnormal) by item, visit, and parameter;
- Shift table of changes in greatest grade from baseline for parameters that can be graded as per CTCAE.

Laboratory abnormalities will be listed.

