5.5.7. Other safety measures

The ECOG PS at baseline and change from baseline will be analyzed by visit and group. Child-Pugh score will be summarized by visit and group (as continuous variable), and analyzed for frequency and percentage (as categorical variable).

The listing of echocardiography results will be provided.

The categories of the greatest post-baseline HBV-DNA values (< 500 , $500-2000$, and ≥ 2000 IU/mL) will be summarized. The proportion of subjects with ≥ 100 -fold ($2\log_{10}$) maximum change in the greatest post-baseline HBV-DNA values relative to baseline will be summarized and the maximum rate of change from baseline will be descriptively summarized. AEs and efficacy in subjects with post-baseline HBV-DNA ≥ 2000 IU/mL will be summarized.

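### SAP 5.1.5 makes no exception for worst-value analyses, so read literally the laboratory abnormality, greatest-grade and greatest HBV-DNA summaries can miss peaks recorded at unscheduled tests

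*SAP*

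**What the plan says.** **The visit rule.** SAP 5.1.5 opens with a general statement: "Summary will be based on the visits filled in eCRF according to protocol predefined, with no need to consider unscheduled visits". If a scheduled visit or examination is missing or its result is invalid, "the unscheduled visit closest to the scheduled protocol visit will be considered as the protocol visit", and each unscheduled visit can be used in this way only once. The section closes with a sentence confined to by-visit analysis, under which "there is no need to present the time points for unscheduled visits".

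**The worst-value outputs.** SAP 5.5.3 lists the incidence of abnormalities, a by-visit shift table and, as a separate item, "Shift table of changes in greatest grade from baseline for parameters that can be graded as per CTCAE". SAP 5.5.7 summarises "The categories of the greatest post-baseline HBV-DNA values" in three bands (< 500, 500–2000 and ≥ 2000 IU/mL), the share of subjects with at least a 100-fold rise, and AEs and efficacy in subjects reaching ≥ 2000 IU/mL. Neither section says which visits supply these maxima.

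**When tests are done.** For hematology and biochemistry the protocol's treatment-period table says: "The test will be conducted within 72 hours prior to each administration". That means D1, D15 and D29 in Group A, and D1 and D22 in Group B. During a dose delay protocol 7.2.2 adds: "Subjects who need delayed dose should be monitored every week, and the frequency of monitoring can be increased when clinically indicated". For liver function: "It is recommended to monitor liver function every three days, until the highest value of AST or ALT starts to decrease". HBV-DNA is scheduled on D1 of each cycle from Cycle 2. Note 4 to the visit tables sets a minimum of one test per 42 days and allows more when clinically indicated.

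**The concern.** A rule that discards unscheduled results suits by-visit tables, where every subject should contribute one value per time point. It does not suit a maximum. A greatest-grade table is meant to show how bad the abnormality became, and the extra tests are the ones ordered because something was already abnormal.

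Safety is part of the study objective and a secondary endpoint, and liver function is a central safety question in this population. If the tables are programmed from the literal text, the values that drove management during a dose delay could be absent from the greatest-grade table. They would still be present in the AE tables and the listings, so the study report could contain outputs that disagree with each other.

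**Working it through.** The documents give no figure on this point, so there is nothing to reproduce. The check sets the sections side by side, establishes the direction, and then asks whether a size can be given.

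**1. Where delay-period tests fall.**
- Treatment-period table: hematology and biochemistry belong to dosing visits. There is no column for monitoring during a delay.
- Protocol 7.1: later doses are counted from the actual date of the previous dose, so the pre-dose tests move with a delayed dose.
- Protocol 7.2.3: dosing resumes, with listed exceptions, on recovery to Grade 1 or below or to baseline. The next pre-dose test will therefore often come after the peak.
- Protocol 7.2.2: the weekly and three-day tests fall in between.

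**2. Direction.** Let A be all post-baseline results for a subject and S the subset admitted by 5.1.5. Since S is contained in A, max(S) ≤ max(A). Likewise, a subject with an abnormal result in S has one in A, so incidence from S cannot exceed incidence from A. The replacement clause does not change this, because it picks the nearest result, not the worst.

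**3. Sampling density per 42 days (42 / interval).**
- Group A dosing visits: 42/14 = 3
- Group B dosing visits: 42/21 = 2
- Weekly monitoring: 42/7 = 6
- Every three days: 42/3 = 14
- Scheduled HBV-DNA: 42/42 = 1

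**4. Illustration on a fixed grid.** Assume (not from the documents) that a peak lasts d days and falls at random against a grid of T days. The chance that at least one sample falls within it is min(1, d/T).

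| T (days) | d = 3 | d = 7 | d = 14 |
|---|---|---|---|
| 3 | 1.00 | 1.00 | 1.00 |
| 7 | 0.43 | 1.00 | 1.00 |
| 14 (Group A) | 0.21 | 0.50 | 1.00 |
| 21 (Group B) | 0.14 | 0.33 | 0.67 |
| 42 (HBV-DNA) | 0.07 | 0.17 | 0.33 |

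The range is wide and is set by d, which the documents do not give.

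**5. Illustration with a dose delay.** Assume ALT starts at 1 × ULN, doubles every 4 days for 14 days (peak 2^(14/4) = 11.3 × ULN), then halves every 7 days. Assume the dose is held once a scheduled test exceeds 3 × ULN, with tests every 3 days after that and no further scheduled test until recovery.
- ALT passes 3 × ULN on day 4·log2(3) = 6.3. It is above 8 × ULN from day 12 to day 17.5, and above 5 × ULN from day 9.3 to day 22.2.
- The scheduled test that triggers the hold falls uniformly over 14 days (Group A) or 21 days (Group B) from day 6.3.
- Recorded above 8 × ULN, scheduled tests only: 5.5/14 = 39% (A) and 5.5/21 = 26% (B). All tests: (17.5 − 6.3)/14 = 80% and (17.5 − 6.3)/21 = 53%. Share retained: 5.5/11.2 = 49% in both groups.
- Recorded above 5 × ULN, scheduled tests only: (20.3 − 9.3)/14 = 79% (A) and (22.2 − 9.3)/21 = 61% (B). All tests: 100% and (22.2 − 6.3)/21 = 76%. Share retained: about 80% in both groups.

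The same assumed course gives a loss of about one half or about one fifth, depending only on the threshold.

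**6. HBV-DNA.** Protocol 7.2.2 does not name HBV-DNA, so the delay mechanism does not apply to it. The route is note 4: a test added because it was clinically indicated is not on the D1 schedule. A peak seen only there would place the subject in a lower band and, where relevant, leave the subject out of the ≥ 2000 IU/mL group.

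**The case against.** **The rule may be meant only for by-visit tables.** It sits under the heading on analysis windows, and most of the section is about assigning results to visits. That reading is available. But the opening sentence is not limited in that way, while the closing one is, and SAP 5.5.3 and 5.5.7 are silent. The point that stands is that the tables can miss peaks, not that they will.

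**Delay-period tests may count as protocol-predefined.** They are written into protocol 7.2.2, and no document says that the eCRF labels them unscheduled. This also stands, and it is a reason to settle the matter in the SAP. The three-day liver testing is only a recommendation.

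**Toxicity is captured elsewhere.** A reader might infer that the trial's toxicity as a whole will be understated. The documents do not support that. SAP 4.2.1 counts clinically significant laboratory abnormalities as TEAEs, including during dose interruption. SAP 5.5.2 makes abnormal hepatic enzymes an event of special interest. Protocol 9.2.3 makes defined hepatic enzyme abnormalities SAEs, and SAP 5.5.3 lists laboratory abnormalities. These safeguards do not repair the laboratory summary tables, because they rest on judgement or on reporting criteria, or are not summarised.

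**Some peaks are on the schedule anyway.** End-of-treatment and on-site safety follow-up visits are predefined and include hematology, biochemistry and virology, so a subject stopped permanently may have a scheduled test near the peak. A scheduled visit missed during a delay also admits one nearby unscheduled result.

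**Size and arm differences.** A reader might infer that half of severe episodes are lost, or that the Q2W versus Q3W comparison is distorted. The one-half figure needs a cut at 8 × ULN, close to an assumed peak, and no SAP laboratory table uses that cut. In the same illustration the share lost is nearly equal in the two groups, and SAP section 3 plans no formal testing.

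**Conclusion.** The point holds as a gap in the SAP's data-handling rules. Followed literally, 5.1.5 leaves out unscheduled results from three kinds of output: the laboratory abnormality incidence table, the greatest-grade shift table, and the greatest HBV-DNA summaries with the subgroup defined from them. The direction is certain: those outputs can equal or fall below the values from all results and can never exceed them.

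The size is not known. It would need peak durations, the frequency of dose delays, and the eCRF labelling of delay-period tests, none of which the documents give. The illustrations show only that the loss could range from small to substantial. The conclusion assumes that at least some tests under protocol 7.2.2 or note 4 are stored as unscheduled. If all were stored as predefined visits, the problem would disappear. The AE-based safety conclusions are not called into question.

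**What to change.** Limit the rule in SAP 5.1.5 to by-visit summaries. Add to SAP 5.5.3 and 5.5.7 a sentence such as: incidence-of-abnormality, greatest-CTCAE-grade and maximum-value analyses, including the HBV-DNA bands, the maximum HBV-DNA change and the ≥ 2000 IU/mL group, use all post-baseline results, scheduled and unscheduled, including those taken during dose delays. Also state how tests done under protocol 7.2.2 are labelled in the eCRF.

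While editing 5.1.5, correct the tie rule: it compares two unscheduled visits but then selects the later scheduled one.

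The cost is a few sentences and minor programming. No additional tests are needed and no clinical rule changes. Reported laboratory toxicity may look slightly less favourable.

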Tumor imaging evaluation	√	√	√	If the subject has no progression of disease when withdrawal from the study, the tumor still has to be evaluated once every 6 weeks according to RECIST v1.1, until progression of disease or start of subsequent anti-cancer therapy. Including the enhanced CT scan at thorax, abdomen, pelvis and site of lesions. In case of allergy to the contrast agent for enhanced CT scan, thoracic plain CT scan + abdominal and pelvic MRI can be performed. Bone scan is only performed when clinically indicated.

Items	End-of-Treatment ^[5]	Follow-up period		Comment
		Safety follow-up ^[6]	Survival follow-up ^[7]	
Others				
Survival information		√	√	
Subsequent anti-cancer therapy		√	√	

Note: [1] All the baseline data will be based on the value closest to the study dose.

- [2] For the subjects who have failed screening and are enrolled during re-screening period, if the visit procedures completed at the initial screening, and meet the required time limit for this procedure prior to start dose of the investigational drug and meet the inclusion criteria, they do not need to repeat the procedure during the re-screening period.
- [3] There's no ± 3 days window period for Day 1 of Cycle 1.
- [4] Starting from Cycle 2, the test will be performed on $D1 \pm 3$ of each cycle or at least once every 42 days, and more frequently when clinically indicated.
- [5] End of Study Treatment/Withdrawal from Study: If these tests/procedures have been completed within 7 days after withdrawal from the study, no further repetition is required.
- [6] Safety follow-up: until 90 days after last dose. During this period, one visit will be performed once every 30 days (± 7 days). The first (30 days after the last dose) and third (90 days after the last dose) safety visit after receiving drugs must be performed at the study center, the second visit (60 days after the last dose) is telephone visit, and only survival data, concomitant medication/therapy, AE need to be collected.
- [7] Survival follow-up: The subjects will enter the survival follow-up period after the end of safety follow-up period. During this period, the subjects will be followed up by telephone once every 30 days (± 7 days) for collection of survival data and subsequent therapies.

ABBREVIATIONS AND DEFINITIONS

The following abbreviations and special terms will be used in the study protocol.

Abbreviation and specific terms	Definition
AE	Adverse event
AFP	Alpha fetoprotein
ALP	Alkaline phosphatase

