5.1.6. Processing of missing date and missing data

Except for special circumstances, the following rules for imputation are applicable to the absence of event date for safety data.

If the date of an event is totally absent, it will not be imputed. If the date is missing, but the year and the month are consistent with that of study treatment, it will be imputed with the date of the first dose of the investigational drug, or first day of that month for other conditions; if the date of the end day is missing, but the year and the month are consistent with that of the end of treatment, the date of the end of event will be imputed with the date of the end of study treatment, or the last day of that month for other conditions.

If the month and the date of an event are missing, but the year is consistent with that of study treatment, they will be imputed with those of the start of study treatment, or 1 Jan. for other conditions.

All the dates imputed must precede the dates of withdrawal of informed consent form, lost to follow-up or death.

Missing data on laboratory tests, ECG, and vital signs will not be imputed.

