5.5.4. Vital signs

Baseline is defined as the last measurement prior to first dose. Vital signs will be summarized using descriptive statistics according to Hengrui's Statistical Analysis Reporting Standards, including but not limited to: descriptive summaries of absolute value and change from baseline at the scheduled visits in the protocol.

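### SAP 5.1.5 fills a missing scheduled result from the closest unscheduled visit with no maximum distance, so descriptive by-visit safety tables can show values measured weeks from the visit named

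*SAP*

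**What the plan says.** SAP 5.1.5 (Analysis window) opens by basing summaries on protocol visits as entered in the eCRF and setting unscheduled visits aside. It then makes an exception. The trigger is broad: "In the case that the scheduled protocol visit is missing, or one examination is missing within the scheduled visit or the result is invalid". In that event "the unscheduled visit closest to the scheduled protocol visit will be considered as the protocol visit".

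Two clauses limit the exception: "All the protocol visits will be scheduled in order", and "Once one unscheduled actual visit has been defined as one protocol visit, it will be no more defined for the other protocol visit". Ties are handled as follows: "If the time to the scheduled visit is equal for two unscheduled visits, the later scheduled visit will be used as the protocol visit". The section ends by saying that by-visit analyses use the scheduled time points and need not show those of unscheduled visits.

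The protocol does have windows. The schedule tables give ±3 days for treatment visits (none for Cycle 1 Day 1) and ±7 days for safety follow-up. Section 7.2.4 gives ±7 days for safety visits and laboratory tests during delays of more than 6 weeks. SAP 5.1.5 refers to none of these.

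The rule feeds the outputs organised by visit: the laboratory normal/abnormal shift table (SAP 5.5.3), vital signs (SAP 5.5.4: "descriptive summaries of absolute value and change from baseline at the scheduled visits in the protocol"), physical examination (5.5.6), and ECOG PS and Child-Pugh score (5.5.7).

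**The concern.** A section on analysis windows would be expected to say how far from its target date a result may lie and still represent a visit. This one gives a rule for choosing among unscheduled results but none for rejecting them. A programmer who follows it exactly must use a single distant result, and the table need not show when that result was obtained.

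The results available for filling are unlikely to be a random sample of the subject's course. Protocol 7.2.2 asks for weekly monitoring while a dose is delayed and recommends liver tests every three days until the transaminases start to fall. Note 4 to the protocol's schedule tables has coagulation, AFP, thyroid and virology tests done on Day 1 "of each cycle or at least once every 42 days, and more frequently when clinically indicated". Extra tests therefore tend to be prompted by a problem. A gap filled from them would plausibly carry an abnormal value, placed at a time when the subject may not have had it. The time course of toxicity in the by-visit tables is what is at stake.

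**Working it through.** The plan gives no figure to reproduce, so the check is date arithmetic on the rule.

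**Inputs from the documents**
- Cycle length 42 days (Protocol 3.2.2). The day of first dose is study day 1 (SAP 5.1.2).
- Thyroid function is tested on Day 1 of each cycle from Cycle 2, window ±3 days (Protocol, treatment-period table).
- Dosing visits are 14 days apart in Group A and 21 days apart in Group B (Protocol 3.2.2).

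**Assumed for the example:** the Cycle 2 Day 1 thyroid test is missed, the only unscheduled thyroid test is on day 70, and Cycle 3 Day 1 is attended on its nominal day.

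**Step 1, nominal days.** Cycle 2 Day 1 = 1 + 42 = day 43. Cycle 3 Day 1 = 43 + 42 = day 85.

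**Step 2, apply the rule.** The examination is missing, so the rule is triggered. Only one unscheduled result exists, so it is the closest. It is used once. Day 70 precedes day 85, so the order of visits is kept. Day 70 is therefore tabulated as Cycle 2 Day 1.

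**Step 3, displacement.** 70 − 43 = 27 days, and 27/3 = 9 times the window. The distance to Cycle 3 Day 1 is 85 − 70 = 15 days, so the value lies nearer to the following visit.

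**Step 4, the alternative timing in note 4.** That note also accepts a test at least once every 42 days. The screening test is no later than day 1, so the gap is at least 70 − 1 = 69 days. The example is outside that allowance too.

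**Step 5, how far the rule reaches when the next visit is attended.** If visits must stay in order, the substitute has to fall before the next attended visit.
- Once-per-cycle tests: up to day 84, so 84 − 43 = 41 days.
- Tests due at every dose: up to 14 − 1 = 13 days (Group A) or 21 − 1 = 20 days (Group B).

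**Step 6, when no later visit is attended.** Count from the last dose, with the next visit due at day 14 (A) or day 21 (B).
- End of a 6-week delay: 42 − 14 = 28 days (A), 42 − 21 = 21 days (B).
- Day 90, the end of safety follow-up: 90 − 14 = 76 days (A), 90 − 21 = 69 days (B).

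These are outer limits. They need the due visit to count as missing and an extra unscheduled test to exist. The day-90 figures also need the scheduled day-30 follow-up visit to be missed, because otherwise the in-order clause blocks them.

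**Step 7, with a cap.** At ±3 days the largest displacement is 3 days, and the example's Cycle 2 Day 1 cell stays missing.

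**Effect on a table (assumed numbers only).** Take 150 subjects tested at a visit, 30% abnormal (45), and 5 gaps filled from unscheduled tests, 90% of them abnormal. The rate moves from 45/150 = 30.0% to (45 + 4.5)/155 = 31.9%. Over the whole possible range for the 5 fills, from none to all abnormal, it runs from 45/155 = 29.0% to 50/155 = 32.3%.

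**The case against.** The strongest reply is that the rule is not unlimited. Under the in-order clause a substitute should not jump past an attended visit. That is a fair reading, and it defeats some examples. A day-100 thyroid result could not stand for Cycle 2 Day 1 if Cycle 3 Day 1 was attended on day 85. It does not defeat the day-70 example, and Step 5 shows that up to 41 days remain possible.

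Next, the anchors move. Protocol 7.1 times each dose from the actual previous dose, so days 43 and 85 are nominal. This stands, and it exposes a further gap: the SAP does not define the target date from which the closest visit is measured.

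Third, a reader might infer a contradiction with SAP 5.1.6, which says "Missing data on laboratory tests, ECG, and vital signs will not be imputed". The documents do not support that. The rule moves a value actually measured in the same subject to another visit label, which is visit mapping rather than imputation. It would help if the SAP said how the two sections fit together, but they do not contradict each other.

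Last, blank cells are not neutral. If visits are missed because of toxicity, refusing the substitute removes abnormal values from the by-visit row. This stands as a cost of the fix. It is acceptable only if those results are kept elsewhere in the safety output.

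**Conclusion.** The concern holds for the descriptive by-visit tables. SAP 5.1.5 has no maximum distance, and no other section of either document supplies one. In an ordinary case that respects visit order the displacement is 27 days against a ±3-day window. The size in practice is unknown, because the documents give no count of missed visits or unscheduled tests. With the assumed numbers above, the change in an abnormality rate is about two percentage points.

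Three stronger conclusions are tempting and go too far:
- A reader might infer that the fills come mainly from subjects with toxicity. The protocol's triggers make this plausible, but a clinically indicated test can have other causes.
- A reader might infer that post-treatment results will regularly enter on-treatment rows. The 30-, 60- and 90-day contacts are scheduled and so cannot be substitutes. An extra unscheduled test is needed, and the SAP does not say that visits falling after discontinuation count as missing.
- A reader might infer a threat to the main conclusions. ORR, OS, adverse event incidence, the greatest-grade CTCAE shift table and the listing of laboratory abnormalities are not organised by visit, and SAP section 3 plans no formal hypothesis testing.

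The tie sentence is a separate small defect. It chooses between two unscheduled visits but names a scheduled one. If it means the later unscheduled visit, it can favour a post-dose value, although Protocol 3.2.2 places the per-dose assessments within 72 hours before dosing.

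**What to change.** In SAP 5.1.5:

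1. Let an unscheduled result stand in for a missing or invalid scheduled one only if it falls within the protocol window of that visit: ±3 days for treatment visits, ±7 days for safety follow-up, and ±7 days for safety visits during delays of more than 6 weeks.
2. Count the target date of a treatment visit from the actual previous dose, in line with Protocol 7.1.
3. Otherwise leave the by-visit cell missing, and keep the result in the listings and the worst-grade summaries. State this expressly, because the opening sentence of 5.1.5 could be read as leaving unscheduled results out of all summaries.
4. Correct the tie sentence to refer to unscheduled visits and, where a dose was given, prefer the pre-dose result.

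The cost is a few sentences in the SAP and a date condition in the visit-mapping program. By-visit tables will have slightly more missing cells, possibly more often in subjects with toxicity. Item 3 keeps those subjects' values in the worst-grade tables and listings.
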